## 15 ABBREVIATIONS

The following is a list of abbreviations that are used in the protocol.

MedDRA	Medical Dictionary for Regulatory Activities
mITT	Modified Intent-To-Treat
MMRM	Mixed-effects Model for Repeated Measures
NCCM	Non-Common Cold Medication
PT	Preferred Term
QoL	Quality of Life
SAE	Severe Adverse Event
SAP	Statistical Analysis Plan
SD	Standard Deviation
SAE	Serious Adverse Event
SE	Standard Error
SOC	System Organ Class
TEAE	Treatment-emergent Adverse Event
WURSS	Wisconsin Upper Respiratory Symptom Survey

The purpose of this Statistical Analysis Plan is to ensure that the data listings, summary tables, and figures which will be produced, and the statistical methodologies that will be used, are complete and appropriate to allow valid conclusion regarding the study objectives.

This SAP is based on the following documents:

Haleon Confidential

CCI Statistical Analysis Plan template v7.0

Protocol 300233 28 Oct 2024 Version 1.0
eCRFs; 03 Dec 2024 Version 1.0

1 Summary of Key Protocol Information

This decentralized study is designed to generate real world data from subjects with cough associated with the common cold, evaluating the effects in two arms with commercially available cough syrups on health-related quality of life (QoL). Arm 1 includes one cough syrup (which can be used day or night) and Arm 2 includes the daytime cough syrup and a nighttime cough syrup.

Robitussin Maximum Strength Cough and Chest Congestion DM (Dextromethorphan HBr, USP 20 mg; Guaifenesin, USP 400 mg) and Robitussin Maximum Strength Cough and Chest Congestion DM + Robitussin Maximum Strength Nighttime Cough DM (Dextromethorphan HBr, USP 30 mg; Doxylamine Succinate, USP 12.5 mg) are marketed cough and congestion syrups used for treatment of cough associated with common cold. Although this is a non-life-threatening condition, it impacts individuals' ability to function normally in day-to-day activities (physical, social, occupational, and emotional).

This study will generate data to support the effectiveness of the Robitussin syrups in the real-world setting to suppress cough among individuals with common cold to understand how the effect can influence their QoL.

1.1 Study Design

This is a longitudinal, randomized, open-label, decentralized clinical study evaluating the effect on QoL factors in subjects with cough associated with the common cold in two arms using Robitussin Maximum Strength in a real-world setting.

Subjects will be randomized into one of two study groups (at a 1:1 ratio):

- Group 1 will take Robitussin Maximum Strength Cough and Chest Congestion DM
- Group 2 will take Robitussin Maximum Strength Cough and Chest Congestion DM + Robitussin Maximum Strength Nighttime Cough DM.

1.2 Study Objectives

Each of the treatment groups will be analyzed separately; there is no comparison between the study groups (daytime product only and daytime/nighttime product combination).

Objectives	Endpoints
Primary Objective	Primary Endpoint
To evaluate the over-time effects of Robitussin on QoL factors and common cold symptoms among individuals	Score change from Baseline to each treatment day in: 
• WURSS-21 total score

Haleon Confidential

CCI Statistical Analysis Plan template v7.0

Objectives	Endpoints
experiencing cough associated with common cold, following up to 8 days of treatment using WURSS-21.	
 • WURSS-21 total symptom domain score • WURSS-21 total QoL domain Score • Each of the WURSS-21 symptom scores (10 items in total) [a] • Each of the WURSS-21 QoL scores (9 items in total)
Secondary Objectives	Secondary Endpoints
To evaluate the over-time effects of Robitussin on QoL factors among individuals experiencing cough associated with common cold, following up to 8 days of treatment, using specific QoL questions.	Score change from Baseline to each treatment day in: 
 • social activities • feeling self-conscious around people • coughing in public • falling asleep • sleeping through the night • energy • motivation
To evaluate the over-time effects of Robitussin on specific QoL questions among individuals experiencing cough associated with common cold, following up to 8 days of treatment, using categorized QoL factors.	Score change from Baseline to each treatment day in: 
 • Sleep quality • Vitality • Physical activities • Social activities
Safety	
To record adverse events (AEs) during study period	Number and percent of patients reporting AEs or serious AEs (SAEs) while on treatment: 
 • Related to product • Not related to product
Exploratory Objectives	Exploratory Endpoints
Subgroup analyses for primary and secondary endpoints.	Subgroup: Exclude subjects who took concomitant medications that are known to have an impact on common cold symptoms

1.3 Treatments

Subjects will be randomized into one of the two study groups:

Group 1: Subjects in this group will take Robitussin Maximum Strength Cough and Chest Congestion DM

- Subjects will be instructed to take per label instructions for up to 8 days or until resolution of symptoms, whichever occurs first
- Dosing: Oral tablets Up to 20 ml (Not to exceed 6 doses in any 24 hour period)

Group 2: Subjects in this group will take Robitussin Maximum Strength Cough and Chest Congestion DM + Robitussin Maximum Strength Nighttime Cough DM

[figure not shown]
- Subjects will be instructed to take the following per label instructions for up to 8 days or until resolution of symptoms, whichever occurs first:
- Dosing: Taken as Oral tablets
 - Robitussin Maximum Strength Cough and Chest Congestion DM (Daytime) - Up to 20 ml*
 - Robitussin Maximum Strength Nighttime Cough DM - Up to 20 ml*

*Not to exceed 4 doses of daytime + 1 dose of nighttime OR 3 doses of daytime in any 24 hour period

Dosing instructions will be followed as listed on the study product commercial label.

1.4 Sample Size Calculation

Sufficient individuals (approximately 372) will be screened to enrol approximately 260 eligible subjects assuming an estimated 23% drop out rate. It is believed that for this study, approximately 200 completed subjects (100 per treatment group) are deemed sufficient to observe an improvement in the WURSS-21.

2 Planned Analyses

2.1 Interim Analysis

No interim analysis is planned.

2.2 Blinded Data Review (BDR):

After completion of database soft lock, a BDR will be conducted. The details of the BDR will be compiled in a separate document. The purpose of the BDR is to assign the study populations outlined in Section 4.2.3 of this SAP. As this study is open label, the term “blind” is used to denote that the population determination will be done without respect to treatment. To ensure analyses are blind, the treatment allocation will not be accessed by the statistician prior to the database hard lock. The BDR will be undertaken on this dataset without the treatment variable.

2.3 Final Analyses

The final planned primary analyses will be performed after the completion of the following sequential steps:

1. All subjects have completed the study as defined in the protocol.
2. All required database cleaning activities including any external data reconciliation have been completed and the database has been locked.

Haleon Confidential

CCI

Statistical Analysis Plan template v7.0

3. All criteria for the database hard lock have been met and the randomization codes have been distributed.

After the database has been locked, the final analyses will consist of two main analyses:

Topline TLFs: After completion of database hard lock, a subset of all TLFs will be generated intended to identify key results of the study as outlined in Appendix 1.

Final Analysis: The final analysis is planned to be completed after completion of Topline TLFs and will include all Topline TLFs.

3 Considerations for data analyses and Data Handling Conventions

3.1 Baseline Definition

For all endpoints the baseline value will be self-completed during the screening and enrolment phase. It will, at a minimum, be the latest pre-treatment scores available for the participant.

3.2 Subgroups/Stratifications

There are no planned subgroup analyses for this study. Any subgroups included in the CSR will be post-hoc and labelled as such.

3.3 Timepoints and Visit Windows

The timepoints and visits for this study are defined in the Table 1: Schedule of Activities. Table 1 will present baseline characteristics of study variables categorized by measurement type. For continuous variables, means and standard deviations (SD) will be reported; for categorical variables, frequencies (n) and percentages (%) will be presented. Supplementary tables may also be generated to display related variables grouped by similar characteristics.

Table 1 Schedule of Activities

All assessments are completed online. Subjects will receive links via email/text to complete questionnaires per the Schedule below.

	May occur same-day [a]									
Counterparty Assessments	Pre-screening	Day 0 (Baseline) (N)	Day 1 (N)	Day 2 (N)	Day 3 (N)	Day 4 (N)	Day 5 (N)	Day 6 (N)	Day 7 (N)	2 Days after Last Dose [j] (N)
Pre-screening Survey	X									
Informed consent (self consent)	X									

	May occur same-day [a]									
Counterparty Assessments	Pre-screening	Day 0 (Baseline) (N)	Day 1 (N)	Day 2 (N)	Day 3 (N)	Day 4 (N)	Day 5 (N)	Day 6 (N)	Day 7 (N)	2 Days after Last Dose [j] (N)
Medical/Medication history [b]		X								
Demographics		X								
ID Verification		X								
WURSS-21 questionnaire [cf] (Baseline, pre-treatment)		X								
Specific QoL Questions (Baseline, pre-treatment)		X								
Eligibility Assessment		X								
Randomization		X								
Study product shipped [c]		X								
Study product use [eg]		X	X	X	X	X	X	X	X	
WURSS-21 questionnaire [f] (post-treatment)			X	X	X	X	X	X	X	
Specific QoL Questions (post-treatment)			X	X	X	X	X	X	X	
Product Usage Diary[h]		X	X	X	X	X	X	X	X	
End of Study Survey [i]									X	
Concomitant Medication Check			X	X	X	X	X	X	X	
Adverse Event/Serious Adverse Event			X	X	X	X	X	X	X	X

QoL, quality of life; WURSS-21, Wisconsin Upper Respiratory Symptom Survey-21.

[a] Pre-screening, Screening and Baseline can occur same day if product is received by subject same day

[b] Medical history including medication history will be self-reported by participant during the virtual visit.
[c] Participant eligibility to be confirmed through assessment of inclusion/exclusion criteria and cold symptoms of at least mild intensity reported on the Baseline WURSS-21 assessment at the time of Screening.
[d] Participant to confirm receipt of study product for study enrollment confirmation and read through detailed instructions regarding product dosing; Counterparty staff will be available to answer any queries regarding product use.
[e] Robitussin: Group 1: Subjects in Group 1 will be instructed to take up to 20 ml of Robitussin per label instructions for up to 8 days or until resolution of symptoms, whichever occurs first. Group 2: Subjects in Group 2 will be instructed to take the following per label instructions for up to 8 days or until resolution of symptoms, whichever occurs first: – up to 20 ml of Robitussin Maximum Strength Cough and Chest Congestion DM – up to 20 ml of Robitussin Maximum Strength Nighttime Cough DM
[f] WURSS–21 to be completed at the time of Baseline/Screening to confirm eligibility as well as daily during treatment (from Day 1 up to Day 7).
[g] Study product (Robitussin) to be shipped only after screening/baseline assessments are completed and eligibility is confirmed; up to 8 days' worth of study product(s) will be shipped together to ensure there is no interruption in study timeline or treatment duration.
[h] Participant will complete an eDiary documenting Robitussin use each day directly through the Citrus ePRO module.
[i] Participant-reported End of Study Survey will be completed at the end of study directly through the Citrus ePRO module. Participants ending product use early will complete the survey one day after their last reported dose; participants dosing on Day 7 will complete the survey on Day 7.
[j] Participant-reported Change in Health will be recorded two days after last study product administration.

4 Data Analysis

Data analysis will be performed by CCI with oversight from HALEON. It is anticipated that the statistical analysis software used will be R version 4.4.2 or newer; Stata Version 18 or later (StataCorp. 2023. *Stata Statistical Software: Release 18*. College Station, TX: StataCorp LLC); or another validated statistical software.

Prior to database closure a Blind Data Review (BDR) meeting will be conducted in which various aspects of the trial will be discussed and agreed, including the exact definitions for the Non-Common-Cold-Medication (NCCM) population. Treatment labels will be masked for this review to avoid any potential sources of bias.

Except as described below, all listings will be produced for all randomized subjects.

4.1 Data Quality

Data cleaning will be ongoing throughout the study lifecycle and will be completed by a data manager prior to completion of the final analysis, raising queries and resolving them prior to the final database lock.

Analysis related to the primary, secondary, and safety objectives will be validated by a second biostatistician. Any discrepancies identified during the output review will be corrected or

HALEON Confidential

CCI Statistical Analysis Plan template v7.0

documented until there are no findings, unless findings can be explained and are agreed upon by the study team. At the end of the study, all data sets used for analysis and final output will be archived.

4.2 Populations for Analysis

4.2.1 Subject Disposition

Subject disposition, including the number of subjects screened, enrolled, and reasons for non-randomization will be summarized in Table 14.1.1. The table will also present the number of subjects who completed the study and reasons for discontinuation. Listing 16.2.1.1 will present subject disposition.

4.2.2 Protocol Deviations

Protocol deviations will be reported as numbers and percentages, with deviations grouped into important and non-important deviations. Important deviation will be summarized (Table 14.1.2) and all deviations will be listed (Listing 16.2.2.1) produced for all randomized subjects.

Subjects with important protocol deviations liable to influence the primary and secondary endpoints may have their affected data excluded from analyses in exceptional circumstances as decided at the BDR meeting. Subjects may also be identified as having important protocol deviations not leading to exclusion of data from analyses.

Important deviations of the protocol procedures may include, but will not necessarily be limited to the following:

- Consent procedures
- Inclusion/Exclusion criteria
- Concomitant medication/therapy
- Study procedures
- Randomization procedures
- Study drug dosing/study product administration/study product compliance
- Visit schedule/interval
- Other

The specific details of the important protocol deviations will be listed and assessment process will be specified in the BDR meeting and subjects with important protocol deviations will be identified at the BDR meeting.

4.2.3 Analysis Populations

The following analysis populations are defined.

Population	Definition / Criteria	Analyses Evaluated
Enrolled Population	All subjects who meet inclusion/exclusion criteria Due to the nature of this study, the enrolled population is equivalent to the randomized subjects .	Enrollment summaries and subject disposition

Population	Definition / Criteria	Analyses Evaluated
Safety Population	All subjects who use either study product at least once. Population will be based on actual study product used (regardless of group).	Analysis of safety variables, subject demographics and baseline characteristics
Modified Intention-to-Treat (mITT) Population	All subjects who use the study product at least once and have at least one post-baseline QoL questionnaire for at least one primary endpoint assessment to support at least one of the primary endpoint assessments	Primary and secondary endpoints. All analyses will be mITT unless otherwise stated.
Non-Common-Cold-Med (nCCM) Population	All subjects in the mITT population who have not used other medicinal products which might influence reported symptom severity. Reported concurrent medications will be assessed in a Blind Data Review (BDR) meeting to identify potentially interfering medications prior to analysis.	Exploratory endpoints

4.3 Subject Demographics and Other Baseline Characteristics

Demographic and baseline characteristics summaries will be produced for the Safety Population.

4.3.1 Demographic Characteristics

Demographic and baseline characteristics for each group will be reported for the Safety Population using descriptive statistics. For categorical variables (sex, smoking status, race, and ethnicity), the number and percentage of subjects in each category will be reported by treatment group. For continuous variables (age, weight, and height), summary statistics will include arithmetic mean, standard deviation, median, interquartile range, and minimum/maximum values by treatment group. All demographic data will be presented in Table 14.1.3 and Listing 16.2.4.1. For repeatedly collected measurements, data will be described at each timepoint.

4.3.2 General Medical History

Self-reported relevant medical and/or surgical history (in the previous 12 months) including allergies or drug sensitivity and prior medications/treatments, including prescription and non-prescription drugs, vaccines, dietary supplements and herbal remedies, that began before obtaining informed consent will be recorded as the Medical History/Current Medical Conditions.

Medical History will be coded using MedDRA. Medical Histories will be summarized by System Organ Class (SOC) and Preferred Term (PT) listed for the safety population (Table 14.1.4). The presence/absence of any relevant medical history will be listed in Listing 16.2.4.2 with start date and end date or ongoing at the start of study product.

4.4 Treatments (Study Product, other Concomitant Therapies, Compliance)

Compliance data will be summarized for the safety population, exposure and other medications will also be summarized on the safety population.

Randomization details will be listed, including the randomization number, the planned study product, the actual study product the subject received and the randomization date (Listing 16.1.7.1) for all randomized subjects.

4.4.1 Study Product Compliance and Exposure

Compliance will be assessed as the number of days subjects reported to have adhered to the treatment regime up the end of treatment. For compliance and analysis tables, the end of treatment will be defined as the last day the subject used the study product or day 7. The number of compliant days will be tabulated using absolute and relative frequencies as well as the mean, standard deviation, minimum and maximum values, median, and quantiles (Table 14.1.6 and Listing 16.2.5.1). A summary of daily product use will also be presented (Table 14.1.7 and Listing 16.2.5.1). Listing 16.2.5.1 will show all study product uses, including subjects who use the study product after Day 7.

4.4.2 Prior and Concomitant Medication

Prior medications/non-drug therapies and concomitant medications/significant non-drug therapies used prior to treatment initiation and in the treatment phase will be tabulated and listed (Table 14.1.5 and Listing 16.2.4.2).

Prior medications/treatments, including prescription and non-prescription drugs, dietary supplements and herbal remedies, taken in the last 30 days and prior to signing the informed consent form, will be documented in the CRF. The prior and concomitant medications will be coded using a validated medication dictionary, CCI

CCI

Prior medications and prior non-drug treatments will be listed by subject, with drug name, CCI Drug Synonym, reason for medication, route, dose, frequency, start date, start day relative to the study product start date, end date and end day relative to the study product start date (Listing 16.2.4.3) for all safety subjects. Prior medications are defined as those which stopped before the first use of the study product.

Concomitant medications and concomitant non-drug therapies taken during treatment will be listed similarly (Listing 16.2.4.2) for all safety subjects with either ongoing or end date displayed. Concomitant medications are defined as medications that started or stopped on or after the first use of the study product or are ongoing.

Unknown dates will not be imputed. However, if the start or stop date is unknown, then it will be assumed to be concomitant medication unless the partial start date or stop date indicates differently.

4.5 Analysis

4.5.1 Primary Endpoint

4.5.1.1 Primary Endpoint Definition

The primary endpoint will be measured using the Wisconsin Upper Respiratory Symptom Survey (WURSS); 21 question daily symptom report.

WURSS-21 scores will be reported as:

- Total score: sum of questions 2 through to 20
- Total symptoms domains score: sum of the items (questions 2 – 11) in the symptom section (10 individual items on cold symptoms answered on a 0 (does not have this symptom) - 7 (severe scale))
- Total QoL domain score: sum of the domains (questions 12 – 20) in the QoL section (9 individual items on cold interference to QoL answered on a 0 (not at all) - 7 (severely scale))
- Individual symptom item score (10 items)
- Individual QoL item score (9 items)

Change from baseline (Day 0) will be calculated for each subject by subtracting the baseline score from scores at subsequent treatment timepoints (Days 1-7 after baseline) regardless of study product use compliance as long as they have used it at least once and at end of treatment (defined as the last day of study product use or day 7 – whatever event comes first). The percentage improvement will be calculated at each timepoint (Days 1-7, and end of treatment), any timepoints after Day 7 will not be included in the analysis tables but will be included in the subject listings. Results will be presented for both the mITT and NCCM populations in:

- Tables 14.2.1.1.1 through 14.2.1.5.2
- Figures 14.2.3.1 through 14.2.6.2

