## 2 STUDY OBJECTIVES AND ENDPOINTS

**Table 2-1 Study Objectives and Endpoints**

Each of the treatment groups will be analyzed separately; there is no comparison between the study groups (daytime product only and daytime/nighttime product combination).

Objectives	Endpoints
Primary	
To evaluate the over-time effects of Robitussin on QoL factors and common cold symptoms among individuals experiencing cough associated with common cold, following up to 8 days of treatment using WURSS-21.	Score change from Baseline to each treatment day in: 
 
• WURSS-21 total score
 
• WURSS-21 total symptom domain score
 
• WURSS-21 total QoL domain score
 
• Each of the WURSS-21 symptom scores (10 items in total)
 
• Each of the WURSS-21 QoL scores (9 items in total)
 

Secondary	
To evaluate the over-time effects of Robitussin on QoL factors among individuals experiencing cough associated with common cold, following up to 8 days of treatment, using specific QoL questions.	Score change from Baseline to each treatment day in: 
 
• social activities
 
• feeling self-conscious around people
 
• coughing in public
 
• falling asleep
 
• sleeping through the night
 
• energy
 
• motivation
 

To evaluate the over-time effects of Robitussin on specific QoL questions among individuals experiencing cough associated with common cold, following up to 8 days of treatment, using categorized QoL factors.	Score change from Baseline to each treatment day in: 
 
• Sleep quality
 
• Vitality
 
• Physical activities
 
• Social activities
 

Safety	
To record adverse events (AEs) during study period	Number and percent of patients reporting AEs or serious AEs (SAEs) while on treatment: 
 
• Related to product
 
• Not related to product
 

Exploratory	
Subgroup analysis for primary and secondary endpoints	Subgroups: 
 
• Excluding subjects who took concomitant medications that are known to have an impact on common cold symptoms
 

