## 5.6 End of Treatment Period

Robitussin product(s) may be used for up to 8 days (Day 0 - Day 7).

Subjects will have the option to discontinue treatment at their discretion. Subjects may choose to discontinue treatment if:

- they feel that their symptoms do not warrant further use of the study product(s), or
- their cough symptoms are considered resolved

Subjects that continue to use the study product(s) will be prompted to discontinue treatment after 8 consecutive days of use and seek advice from their general physician for further assessment and treatment.

Subjects will also be informed that the study will end on Day 7 (or the day after the last treatment, if earlier than Day 7), and will be asked to fill in an End of Study survey.

Subjects will be informed that a Change in Health survey will be sent 2 days after their last study product dose (day 9 at latest) and will be asked to report any changes in their health post-completion of the study.

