4.5.1.2 Statistical Hypothesis, Model, and Method of Analysis

Changes in WURSS-21 domain and total scores from baseline will be analyzed using a linear mixed-effects model for repeated measures (MMRM) with subjects as the clustering unit. The model will include treatment day (as a categorical variable up to day 7) and baseline WURSS-21 score as fixed effects, with a random intercept for each subject. The model will employ an unstructured covariance matrix for within-subject variance-covariance errors, Kenward-Rogers degrees of freedom, and restricted maximum likelihood estimation (REML). For each treatment group, the following will be reported at each treatment day: estimated marginal mean differences from baseline on the original scale, standardized effect sizes (where applicable) with 95% confidence intervals, and nominal p-values. Primary endpoints will be evaluated at the 5% significance level. Given the study design, no adjustments for multiple comparisons will be made.

The distribution of outcome measures will be assessed for normality using Q-Q plots for each treatment group. While linear mixed-models are generally robust to modest departures from normality, substantial deviations (as assessed through visual inspection of Q-Q plots and formal tests including Shapiro-Wilk test) will prompt complementary analyses using

non-parametric methods. The Wilcoxon signed-rank test will be conducted at each timepoint, including end of treatment, as a sensitivity analysis to the primary MMRM analysis. If substantial discrepancies (defined as >20% difference in effect estimates or divergent statistical significance at $\alpha=0.05$) are observed between the MMRM and Wilcoxon signed-rank test results, both sets of results will be reported with appropriate discussion of the differences. For the primary analysis, the MMRM results will be considered primary, with non-parametric results serving as supportive evidence. Model diagnostics will include assessment of heteroscedasticity through residual plots. If significant heteroscedasticity is detected (defined as systematic patterns in residual plots or significant Breusch-Pagan test results at $\alpha=0.05$), Huber-White robust standard errors will be applied to ensure valid inference. All model assumption violations and remedial measures will be documented in the statistical analysis report.

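### The SAP tests change at an end-of-treatment day that the subject chooses on symptoms and that has no counterpart in the MMRM; it should be descriptive only

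*SAP*

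**What the plan says.** Protocol Table 2-1 gives the primary endpoint as "Score change from Baseline to each treatment day in" the WURSS-21 total, the two domain totals and the individual items. Protocol 8.3.2 and the SAP objectives table (1.2) say the same. None of them names an end-of-treatment value.

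SAP 4.5.1.1, the primary endpoint definition, adds one: "the last day of study product use or day 7", whichever comes first. SAP 4.5.1.2 then says: "The Wilcoxon signed-rank test will be conducted at each timepoint, including end of treatment, as a sensitivity analysis to the primary MMRM analysis". The paragraph on summary statistics that closes 4.5.1.2 asks for 95% confidence intervals at end of treatment as well as on Days 1 to 7.

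The MMRM in 4.5.1.2 has "treatment day (as a categorical variable up to day 7" as its time factor and no end-of-treatment term. The same section ranks the two methods: "the MMRM results will be considered primary, with non-parametric results serving as supportive evidence".

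Protocol 5.6 leaves stopping to the subject. It names two reasons: symptoms no longer call for the product, or "their cough symptoms are considered resolved". Under Protocol 5.5, early stoppers fill in forms until one day after the last dose. SAP Section 5 excludes flagged data reported after stopping from all analysis tables. It does not list the added timepoint as a change from the protocol.

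**The concern.** There are two separate problems.

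The first is logical and needs no model. A sensitivity analysis re-estimates the same quantity under other assumptions. Change at a day that differs between subjects is not a quantity the MMRM estimates. The SAP's discrepancy rule (effect estimates more than 20% apart, or significance that diverges at 0.05) therefore has nothing to be compared with at end of treatment. Setting that result against the Day 7 MMRM estimate would compare two different quantities.

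The second is selection. The score is read on a day that the subject picks partly because of how the symptoms stand. A fluctuating score read at a favourable moment shows improvement even when the mean is flat. Read just before that moment, it shows the reverse.

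At stake is a set of supportive p-values and intervals that sit in the primary endpoint tables. There are 3 + 10 + 9 = 22 primary scores and two groups, so up to 22 x 2 = 44 end-of-treatment p-values per analysis population, and they would be easy to quote as confirmation.

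**Working it through.** **Plan figures.** The documents give no SD, day-to-day correlation, effect size or distribution of stop day, so there is no end-of-treatment figure to reproduce. The one usable input is 100 completers per group (SAP 1.4). Its enrolment figure reproduces: 200 / (1 - 0.23) = 259.7, or 260. The test level is 5% ("Primary endpoints will be evaluated at the 5% significance level", SAP 4.5.1.2), taken here as two-sided.

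**Formula.** Let T be the smaller of the last day of use and 7. The end-of-treatment change is Y(T) - Y(0), with mean

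sum over t of P(T = t) x E[ Y(t) - Y(0) | T = t ].

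If T is independent of the scores, this is a weighted average of the fixed-day means, and it is zero when they are all zero. If T depends on the scores, the conditional means are not the fixed-day means, and the sum need not be zero.

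**Assumed model.** The score has unit SD and zero mean change on every day, with Y(t) = rho x Y(t-1) + sqrt(1 - rho^2) x noise and rho from 0.7 to 0.9. There are 100 subjects. A subject stops on the first day the score is 0.5 or 1 SD better than baseline. The end-of-treatment change is tested by a two-sided Wilcoxon test at 0.05.

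| Case | Mean change at end of treatment (truth 0) | Rejection |
|---|---|---|
| Last use on the better day | about -0.05 to -0.28 SD | 11% to 81% |
| Same, endpoint correlated 0.4 with the score that drives stopping | -0.02 to -0.12 SD | 6% to 28% |
| Last use the day before | about +0.13 to +0.16 SD | 7% to 16% |

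**Wider settings.** These add a subject effect, other correlations and other stopping rules.
- Stopping unrelated to symptoms: 0.00 SD, 5.4% rejection.
- Stopping equally on better or worse scores: 0.00 SD, 6.7%.
- Stopping only on worsening: +0.20 SD, 51%.
- Gradual dependence on the score, last use on the better day: -0.05 to -0.19 SD, 9% to 43%.
- Gradual dependence, last use the day before: +0.01 to +0.05 SD, 4% to 6%.
- Sharp threshold, last use on the better day: -0.17 to -0.49 SD, 51% to 99%.
- Sharp threshold, last use the day before: +0.14 to +0.35 SD, 16% to 100%.

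Part of the gap between the two day-before ranges is a convention. The table reads a subject who feels better on Day 1 at Day 1. The wider setting counts that subject's last use as Day 0, with zero change. The SAP has no rule for this case, although its Table 1 allows product use on Day 0 and starts post-treatment forms on Day 1.

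**Fixed days under the same stopping.** Full follow-up would keep the Day 7 Wilcoxon test at 3.9% to 5.7% in the flat model, but this trial does not have it. With forms ending one day after the last dose, the observed-case Day 7 Wilcoxon gives +0.27 to +0.93 SD and 67% to 100% rejection in the table's model. In the wider settings it gives +0.08 to +0.63 SD and 11% to 98%. A maximum-likelihood estimate under missing at random, which is what the MMRM targets, stays at -0.001 to +0.005 SD in those wider settings.

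**The case against.** The strongest reply is that little depends on this test. The MMRM is primary, the Wilcoxon result is supportive, and no decision rule or sample size uses end of treatment. The Wilcoxon sentence can also be read as applying only after non-normality. All of that stands, and it limits the weight of the point. A reader who sees the definition under the primary endpoint heading might infer that the primary analysis is biased. The documents do not support that, because the MMRM contains no end-of-treatment term.

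Second, the size rests on assumptions. Stopping follows cough, while most of the scores are totals or other items, and at a correlation of 0.4 the bias falls by more than half. Protocol 10.1 also lists lack of efficacy and adverse events as reasons for discontinuation, which need not follow improvement. This stands too. A reader might infer that the test is tilted in favour of the product, but the direction depends on whether the last dose falls on the better day or the day before, and no rule fixes that.

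Third, a flat mean is not this trial's situation. Colds resolve (Protocol 3.2), and entry requires a cough score of at least 5 (Protocol 4.3), so regression to the mean moves fixed-day changes as well. It follows that removing this test does not restore a 5% level for the within-group tests. Nor would the remaining fixed-day Wilcoxon tests be sound, as the Day 7 results show.

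Fourth, status at last use is a reasonable on-treatment summary. As a descriptive row it is. That does not make it a check on the MMRM or justify a test against zero.

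**Conclusion.** The point holds as a limited one. The SAP adds a timepoint that the protocol endpoint does not have, does not record the addition in Section 5, and attaches a test and confidence intervals to it. The test is called a sensitivity analysis to a model that has no matching estimate. That part rests on the text alone.

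The reading day also depends on the outcome. Under a flat mean, with stopping driven by the score itself and 100 subjects per group, the bias is about -0.05 to -0.28 SD or about +0.13 to +0.16 SD, according to which day counts as last use. It is smaller for scores loosely tied to cough and about zero if stopping is unrelated to symptoms. These figures show that the test can fail and in which directions; they do not forecast this trial's result. The primary MMRM for Days 1 to 7 is not affected.

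**What to change.** - In SAP 4.5.1.2, remove the mention of end of treatment from the Wilcoxon sentence.
- In the summary-statistics paragraph of 4.5.1.2, remove the end-of-treatment confidence intervals. Show that change as a descriptive row beside the distribution of stop day and reason for stopping, and say how a subject whose last use is on Day 0 is shown.
- List the added timepoint in SAP Section 5.
- Keep the Day 1 to Day 7 MMRM as the basis for inference. Where a fixed-day Wilcoxon result is kept as the fallback of Protocol 8.3.2, label it observed-case and subject to the same symptom-driven stopping, because forms end one day after the last dose and flagged later data are excluded.
- Do not state that the change restores a 5% level.

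The cost is SAP wording and the loss of one supportive p-value and interval per score and group. No data collection changes.
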